## PROTOCOL TITLE: SAFE AND HEALTHY SCHOOLS

participants have completed the research procedures within the target timeframe.

We will continue enrolling participants with positive at-school BinaxNOW test results until 50 participants have nasal and lollipop PCR results.

### 5.0 Inclusion and Exclusion Criteria

#### 5.1 Eligibility Screening:

This study will enroll MMSD school children ages 4-19 and MMSD staff who currently have at least one symptom of COVID-19, have not had a positive COVID test within the past 3 months, and will undergo nasal PCR testing at an MMSD elementary school.

If symptomatic MMSD school children or staff intend to have nasal swab PCR tests at school, then school-approved personnel may inform adults—staff or children’s parents—of our research study. The staff will either provide a flyer or verbally let them know it involves a lollipop test at that time, and if the at-school BinaxNOW is negative, it will also involve the performance of an at-home BinaxNOW test in approximately 24 hours. If the school does not conduct a BinaxNOW test, then the study team will collect a nasal swab for the “at-school” BinaxNOW test.

If the study team does not have any BinaxNOW tests due to a supply shortage, the at-school and at-home BinaxNOW tests will be dropped and participants will be recruited for a Lollipop Only alternative. Additionally, if a potential participant expresses interest in the study but is unwilling or unable to do at-home BinaxNOW testing, then the study coordinator will offer them the Lollipop Only alternative.

School-approved personnel will also let potential participants know that they would not be eligible to participate if they have had a previous positive COVID-19 test in the past 3 months, either verbally or by providing a flyer. The staff will ask if the adult is interested in speaking to a study coordinator to learn more about the study. If yes, the staff will either direct the potential participant to the study coordinator or they will inform the study coordinator that a potential participant is interested in speaking with them, and they will connect the coordinator to the potential participant, either on the phone or in person.

Alternatively, the study team may gently approach potential participants near the at-school testing locations. Potential participants may also directly contact the study team in response to poster and flyer advertisements.

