### 3.2 Hypotheses to be tested:

**Aim 1.1:** “At-home” BinaxNOW testing will be feasible for families.

**Aim 1.2:** Serial “at-home” BinaxNOW testing is non-inferior to “at school” single PCR testing.

**Aim 2.1:** Lollipop swabs are more acceptable to individuals than nasal swabs.

**Aim 2.2:** Lollipop swabs will perform as well as nasal swabs with PCR-based testing.

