## PROTOCOL TITLE: SAFE AND HEALTHY SCHOOLS

Once an interested participant is identified, the study coordinator will review eligibility criteria and explain more details about what is involved. They will let them know what the exclusion criteria are and tell them that prior to enrolling in the study, they do not need to disclose whether they have received a positive COVID-19 test. The coordinator will ask, after the potential participant has learned more about the study and had a chance to ask questions, whether they are eligible and interested in participating. If they decline, the study coordinator will not ask for more details about why they do not wish to participate. In other words, study coordinators will be careful not to probe about COVID-19 diagnoses prior to enrollment. If a potential participant indicates that they are interested in participating but are unable or unwilling to complete the at-home BinaxNOW testing, then the study coordinator will present the Lollipop Only alternative. They will also have this conversation in a setting that is as private as possible. If the potential participant says that they are eligible and interested in participating, the study coordinator will conduct verbal consent with the adult and assent with the child, when applicable. The study coordinator will record the participant's name and information after consent and assent are complete. This study will not track information or explanations from participants who decline enrollment.

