## 8.0 Consent/Accent Process

- 8.1 A trained study team member will obtain informed consent from all adult participants and all parent/legal guardians of child participants. The trained study team member will also obtain assent from all children. If a parent or legal guardian chooses to enroll more than one child in the study, the consent and assent process will be completed for each child enrolled. Children ages 4-14 will be assented using the Assent Script. Children ages 15-17 will be assented using the Consent Script. There will be minor differences in assent discussions depending on children's ages, as study team members will use age-appropriate language.

If the study team does not have a supply of BinaxNOW tests, or if a potential participant is unwilling or unable to complete at-home BinaxNOW testing, the Lollipop Only consent and assent will be used.

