## 13.0 Procedures Involved

13.1 Study Design: This is a quantitative community-based study, conducted in the K-12 setting with school children 4-19 years old, teachers, and staff.

If a participant's initial at-school BinaxNOW test is **positive**, then they will only complete the lollipop swab for PCR testing. They will NOT do the at-home BinaxNOW test virtual visit.

If a participant's initial at-school BinaxNOW test is **negative**, then they will complete both the lollipop swab for PCR testing AND an at-home BinaxNOW test approximately 24 hours later.

If the study team does not have any BinaxNOW tests due to a supply shortage, or if a potential participant is unwilling or unable to complete at-home BinaxNOW testing, the BinaxNOW procedures will be dropped and only the lollipop swab will be collected.

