## PROTOCOL TITLE: SAFE AND HEALTHY SCHOOLS

the client's backup routine. If files are accidentally backed up, they will be manually removed from the backup and deleted permanently from all locations except REDCap. Additionally, the SMPH VPN via the Palo Alto Global Protect client, configured and available for use on all DOP endpoints, will be enabled and connected by the end-user on data collection endpoints whenever study data is being accessed or transferred.

The study team will make every effort to enter data directly into REDCap in real time. The study team will use a wireless hotspot for reliable internet connectivity, rather than relying solely on the school's Wi-Fi connection, to minimize the need for this emergency data collection protocol.

After this basic information is collected, the study coordinator will begin testing. If the participant did not already receive an at-school BinaxNOW test, then the study coordinator will collect the nasal swab for and administer the BinaxNOW test. When study staff collect the nasal swab for the BinaxNOW test, they may encourage parents/legal guardians to comfort their child. Participants under the age of 18 will only receive nasal swabs when their parent or legal guardian is physically present. If a potential participant is unwilling to have the study team collect a nasal swab, they will not be enrolled in the study.

Next, the study coordinator will guide the participant through completing a "lollipop" swab at school. The lollipop swab is obtained by having the participant suck on a swab for 20 seconds in the same way that they would suck on a lollipop. The study coordinator will ask whether they prefer the PCR nasal swab or lollipop collection method. The study coordinator will provide the lollipop swab to Exact Sciences or ACL for analysis. For Exact Sciences, it will be labeled with the study ID and date of collection. For ACL, lollipop samples will have a label and accompanying requisition form that will both contain the subject's full name, date of birth, and the date and time of collection.

If the study team does not have any BinaxNOW tests due to a supply shortage, study participation will end after the lollipop swab is collected. If BinaxNOW tests are available and the participant intends to do the at-home antigen testing, then the at-school antigen testing is required.

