## PROTOCOL TITLE: SAFE AND HEALTHY SCHOOLS

If a participant is unwilling or unable to complete an at-home BinaxNOW test, then their study participation is complete after providing the lollipop swab for PCR testing.

For the at-home BinaxNOW testing, the participant will schedule a follow-up virtual visit with the study coordinator. If they are unable to complete a virtual visit, they will schedule an in-person home visit. They will also be sent home with a BinaxNOW testing kit.

The study coordinator will send participants a confirmation email with a unique link to a secure video chat platform, such as Microsoft Teams, Cisco WebEx, or HIPAA-Secure Zoom. They will also send instructions about how to join the meeting link. During the virtual visit, the study coordinator will instruct the family to read the instructions in the BinaxNOW box, do their best to do the test accurately, and ask questions as needed. The study coordinator will also ask if the participant understands and feels comfortable with the instructions, and the study coordinator will offer to demonstrate the steps of the test. The study team member will use the video to observe sample collection and offer tips or suggestions, as needed, to ensure proper collection. They will also ensure that participants take time and care to read the test results accurately, and they will answer any questions that participants may have. The participant or their parent will verbally provide the test results to the study team, and the study team will record the result in REDCap. The completed test card will be observed and the results verified by the study coordinator.

If a participant is unable or unwilling to do a virtual visit for at-home testing, such as they do not have access to technology or do not wish to provide an email address, they will be offered an in-person home visit. The procedures would be the same. If participants are not able to complete the test during the virtual visit, such as inability to collect the sample or accidental tampering with the test card, the study team member will also provide the option of a home visit. At home visits, if participants are unable or unwilling to collect the nasal swab sample themselves, the study coordinator may collect the sample.

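### Feasibility of at-home testing would be judged among people who had already said they could do it, because those unwilling or unable are enrolled as Lollipop Only with no listed reason for entry

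*Combined protocol and SAP*

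**What the plan says.** **The objective.** Section 1.0 lists feasibility of at-home testing for families as primary objective (1). Section 3.2 states Aim 1.1 as a hypothesis, that at-home "BinaxNOW testing will be feasible for families", without a threshold, estimator or denominator. Section 20 adds none.

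**The route for people who cannot or will not test at home.** Section 5.1 says that if someone shows interest but is "unwilling or unable to do at-home BinaxNOW testing, then the study coordinator will offer them the Lollipop Only alternative". This happens before consent. The revision history introduces it in May 2022 (Revision 8).

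**The route for kit shortage.** The same section says that when kits run out "the at-school and at-home BinaxNOW tests will be dropped and participants will be recruited for a Lollipop Only alternative". The revision history introduces this in January 2022 (Revision 6). Section 13.1 joins the two triggers in one sentence, beginning "If the study team does not have any BinaxNOW tests due to a supply shortage, or if a potential participant is unwilling or unable". Section 8.1 gives both the same paperwork: "or if a potential participant is unwilling or unable to complete at-home BinaxNOW testing, the Lollipop Only consent and assent will be used".

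**What is recorded.** The data elements in Section 13.4 include dates, results and opinions on collection methods, but no reason for entering Lollipop Only. Under Section 13.3 the coordinator asks whether help was needed, and whether the person could test alone in future, once the at-home result has been recorded. Sections 5.2, 5.3 and 20.3 limit the Aim 1 sample to people who completed the at-home test within 72 hours.

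**The concern.** Whether families can do a test at home depends partly on those who say at the outset that they cannot or will not. Since May 2022 the protocol has enrolled such people, but in a group that is not asked to test at home. It places them with shortage entrants, who say nothing about feasibility. If the two kinds of entry are not told apart, neither can be used properly: counting all Lollipop Only entries as failures would be unfair to the method, and counting none would flatter it.

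This differs from non-completion among those enrolled for at-home testing. Those people can be identified, because Section 4.3 replaces them and Section 15.1 withdraws them at 120 hours. A denominator of everyone enrolled for at-home testing would bring them back. It would not bring back people who left the pathway before it began. What is at stake is the answer to a primary objective.

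**Working it through.** **1. The plan's own figure.** Section 20.2 gives N = 358 for a null NPV of 91%, a true NPV of 95%, 90% power and one-sided alpha of 0.05.

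- Exact binomial: 358 is the smallest N with at least 90% power. The rule is success if at least 335 of 358 are true negatives, with alpha 0.0487 and power 0.909.
- Normal approximation: (1.645 × √(0.91 × 0.09) + 1.282 × √(0.95 × 0.05))² / 0.04² = 351.6, so 352.

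The figure reproduces. It powers the NPV test, not feasibility, and nothing here changes it.

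**2. Who can contribute to feasibility as written.**

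| Group | Leaves the at-home pathway | Identifiable from the listed data? | Asked the ability questions? |
|---|---|---|---|
| Completed at-home test | Does not leave | Yes | Yes |
| Enrolled for at-home testing, not completed | After enrolment (4.3, 13.3, 15.1) | Yes | No, if no result |
| Unwilling or unable, said before consent | Before enrolment (5.1, 8.1) | As Lollipop Only, reason not listed | No |
| Kit shortage | Before enrolment (5.1) | As Lollipop Only, reason not listed | No |

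The third row bears directly on feasibility and is the one that cannot be separated from the listed elements.

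**3. How far dates help.** Only the shortage route existed from January to May 2022, so Lollipop Only entries in that period should be shortage entries. From May 2022 both routes are open. A shortage affects the whole study team and changes the recruitment materials (Section 7.4), so stock records and activity dates can classify some later entries. They give no distinction between unwilling and unable.

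**4. Scale, with the count assumed.** Let A be participants who accept at-home testing, C those who complete it in time, and L the Lollipop Only entries who were unwilling or unable while kits were in stock. The documents give planned values A = 400 and C = 358 for school-negative participants, and no value for L.

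- Completion among those enrolled: C/A = 358/400 = 89.5%. This is an enrolment allowance, not an estimate.
- Acceptance: A/(A + L). For L = 20, 60 and 100 (assumed): 400/420 = 95.2%, 400/460 = 87.0%, 400/500 = 80.0%. If the 50 school-positive participants had also accepted before their result was known, A = 450, giving 450/470 = 95.7%, 450/510 = 88.2%, 450/550 = 81.8%.
- Combined into one ratio: if a fraction q of L would have been school-negative, it is 358/(400 + qL). With q = 1 it is 85.2%, 77.8% and 71.6%; with q = 0 it stays at 89.5%. Lollipop Only drops the study's BinaxNOW procedures (Section 13.1), so q is generally unknown. This is why two separate figures are safer than one.

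**The case against.** **The form may already hold the reason.** The full data collection form is not in the documents, and the Section 13.4 list is not exhaustive: it omits date of birth, gender, race and ethnicity, which Section 13.3 says are collected. A reader might infer that the reason is certainly unrecorded and the loss beyond repair. The documents do not support that. What stands is that no reason is listed, and that dates and stock records separate the groups only in part.

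**Feasibility may mean something narrower.** Section 3.1 speaks of volunteer families and of performing and reporting the test accurately, and the questions in Section 13.3 fit that. This is a fair reading, and unwillingness to join a supervised research visit is not the same as inability to test. Home visits, with the coordinator able to take the swab, also reduce inability among those enrolled. But the hypothesis is worded for families without restriction, and no endpoint narrows it. Reporting completion and acceptance separately serves both readings.

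**The later exit in Section 13.3.** The text says "If a participant is unwilling or unable to complete an at-home BinaxNOW test, then their study participation is complete after providing the lollipop swab". A reader might count these people as lost too. In context they are most naturally participants already enrolled with a negative school test. Section 15.3 anticipates people who are asked to test at home and do not, and a denominator of all those enrolled would include them.

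**People who decline everything.** Section 5.1 states: "This study will not track information or explanations from participants who decline enrollment". A reader might want them counted as refusals of at-home testing. That inference fails: the rule lets people with a recent positive test decline without disclosing it, so a count would mix ineligible people with refusers and would sit badly with the rule's purpose.

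**Conclusion.** The point holds. As written, the plan would judge feasibility among people who had already said they could test at home, and the result would tend to be too favourable. The direction follows from the routing in Sections 5.1 and 8.1 and the timing of the questions in Section 13.3.

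The size cannot be stated. It depends on how many people took the unwilling or unable route from May 2022 onward, and the documents give no count. The percentages above show scale under assumed counts. A reader might take 71.6% or 77.8% as the corrected feasibility rate, but those ratios set a planning allowance among school-negative participants against invented counts of people whose school result may be unknown.

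The conclusion rests on two assumptions: that the form has no reason field beyond the Section 13.4 list, and that Aim 1.1 is meant to speak for families in general. If the form does hold a reason code, only the definitions of the denominators remain to be written.

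**What to change.** 1. **Reason code.** Record one for every Lollipop Only entry: no kits, unwilling, or unable. Code past entries from activity dates and stock records where possible, and report how many stay unclassified.
2. **Figure (a), completion.** The proportion completing within 72 hours among all school-negative participants enrolled for at-home testing. Those who stop under Section 13.3, or are replaced or withdrawn, count as non-completers.
3. **Figure (b), acceptance.** The proportion accepting at-home testing among all consented participants offered it while kits were in stock. Lollipop Only entries coded unwilling or unable count as not accepting; shortage entries are left out. Do not require that people were actually asked to test at home: only school-negative participants are asked (Section 13.2), so that condition would remove the pre-consent group again. Show (b) separately from May 2022, since before then the unwilling or unable route did not exist and such people could not appear in it.
4. **Families and staff.** Report child participants separately from staff, because Aim 1.1 concerns families.
5. **No tally of people who decline the study**, for the reason given above.

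The cost is one form field, a short back-coding exercise and a paragraph in Section 20. The downside is a less favourable feasibility figure. The sample size and testing procedures do not change.

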## PROTOCOL TITLE: SAFE AND HEALTHY SCHOOLS

Once an interested participant is identified, the study coordinator will review eligibility criteria and explain more details about what is involved. They will let them know what the exclusion criteria are and tell them that prior to enrolling in the study, they do not need to disclose whether they have received a positive COVID-19 test. The coordinator will ask, after the potential participant has learned more about the study and had a chance to ask questions, whether they are eligible and interested in participating. If they decline, the study coordinator will not ask for more details about why they do not wish to participate. In other words, study coordinators will be careful not to probe about COVID-19 diagnoses prior to enrollment. If a potential participant indicates that they are interested in participating but are unable or unwilling to complete the at-home BinaxNOW testing, then the study coordinator will present the Lollipop Only alternative. They will also have this conversation in a setting that is as private as possible. If the potential participant says that they are eligible and interested in participating, the study coordinator will conduct verbal consent with the adult and assent with the child, when applicable. The study coordinator will record the participant's name and information after consent and assent are complete. This study will not track information or explanations from participants who decline enrollment.

### 5.2 Criteria that define who will be included in the final study sample:

For Aim 1, participants with a negative at-school BinaxNOW test and nasal PCR results who complete both the lollipop PCR and at-home BinaxNOW tests within 72 hours will be included in the final study sample.

Aim 2 will include participants who provide a lollipop swab that is successfully resulted at Exact Sciences or ACL.

### 5.3 Criteria that define who will be excluded from the final study sample:

If certain samples do not provide a result—such as if samples are missing, compromised, or invalid—the subject will not be included in analyses for one or both of the study aims. Criteria for exclusion from analyses are as follows:

Aim 1

-Missing nasal PCR result

-Do not successfully complete an at-home BinaxNOW test within 72 hours of the at-school BinaxNOW test

Aim 2

-Missing nasal PCR result

-Missing lollipop PCR result

## 6.0 Special Populations

### 6.1

- Children/Minors (HRP-416 - CHECKLIST - Children)
- Pregnant persons / fetuses (HRP-412 - CHECKLIST - Pregnant Women; HRP-413 - CHECKLIST - Non-Viable Neonates; HRP-414 - CHECKLIST - Neonates of Uncertain Viability)
- Prisoners (HRP-415 - CHECKLIST - Prisoners)
- Participants with impaired decision-making capacity (HRP-417 - CHECKLIST - Adults with Impaired Decision-Making Capacity)

This study will enroll MMSD students ages 4-19, staff and teachers. This research involves no greater than minimal risk to individuals, including children. It is necessary to enroll children in this study to determine what types of tests are optimal in school settings. Verbal assent will be obtained from all children enrolled in the study after their parent or legal guardian provides consent.

